APPENDIX IV: DRY EYE SYMPTOM QUESTIONNAIRES

The following subject-completed symptom assessments will be collected as noted in Appendix I prior to any other clinic assessments to minimize bias.

- SANDE, Part 1 will be conducted at Visits 1, 2, 3, and 4, and Part 2 at Visit 2, 3, and 4.
- SPEED will be conducted at Visits 1, 2, 3, and 4
- 7-item symptom questionnaire will be conducted at Visits 1, 2, 3, and 4

SYMPTOM ASSESSMENT IN DRY EYE QUESTIONNAIRE (SANDE) (Schaumberg, 2007)

Part 1

PLEASE COMPLETE THE FOLLOWING QUESTIONS REGARDING THE FREQUENCY AND SEVERITY OF YOUR DRY EYE SYMPTOMS
1. Frequency of symptoms:
Please place an 'I' on the line to indicate how often , on average, your eyes felt dry and/or irritated over the past day:
Rarely ————————————————————————————————————
2. Severity of symptoms:
Please place an 'I' on the line to indicate how severe , on average, you feel your symptoms of dryness and /or irritation were over the past day:
Very Mild ———— Very Severe

Instructions for scoring; Part 1. Measure the distance (in mm) between the left end of the line and the mark scored by the subject.

Part 2 (administer at only Visits 2, 3, and 4)

PLEASE COMPLETE THE FOLLOWING QUESTIONS REGARDING TREQUENCY AND SEVERITY OF YOUR DRY EYE SYMPTOMS	THE
1. Frequency of symptoms:	
Please place an 'I' on the line to indicate how often, on average, yo dry or irritated now compared to at your last visit approximately 2 was a compared to a compared t	•
Much less Frequent Last Visit	Much more frequent
2. Severity of symptoms:	
Please place an 'I' on the line to indicate how severe, on average, your symptoms of dryness and irritation are now compared to at your approximately 2 weeks ago	•
Much less severe Last Visit	Much more severe

Instructions for scoring; Part 2. Measure the distance (in mm) between the "Last Visit" anchor at the center of the scale and the mark scored by the subject. If the mark is placed to the right of the anchor, the score will be assigned a positive value (e.g. +10). If the mark is to the left of the anchor, the score will be assigned a negative value (e.g. -15)

SPEED QUESTIONNAIRE (Ngo, 2013 and Korb, 2005)

1. Report the type of SYMPTOMS you experience and when they occur:

	At this Visit		Within the past 72 hours		Within past 3 months	
Symptoms	Yes	No	Yes	No	Yes	No
Dryness						
Grittiness or Scratchiness						
Soreness or Irritation						
Burning or Watering						
Fatigue						

2. Report the FREQUENCY of your symptoms using the rating list below:

Symptoms	0	1	2	3
Dryness				
Grittiness or Scratchiness				
Soreness or Irritation				
Burning or Watering				
Fatigue				

0 = Never **1** = Sometimes **2** = Often **3** = Constant

3. Report the SEVERITY of your symptoms using the rating list below:

Symptoms	0	1	2	3	4
Dryness					
Grittiness or Scratchiness					
Soreness or Irritation					
Burning or Watering					
Fatigue					

0 = No problems

1 =Tolerable; not perfect, but not uncomfortable

2 = Uncomfortable; irritating, but does not interfere with my day

3 = Bothersome; irritating and interferes with my day

4 = Intolerable; unable to perform my daily tasks

7-ITEM SYMPTOM QUESTIONNAIRE

Please rate each of the following symptoms by drawing a line "I" on the scale where: 0 = no discomfort 100 = maximal discomfort Eye dryness **Burning/Stinging** Photophobia Foreign Body Sensation 0 ______100 **Blurred Vision** 0 ______100 Itching Pain 0 ————————————————100

Note: For copying purposes, each line should be 100mm or 3.937 inches.

APPENDIX V: LABORATORY ANALYTES

Serum Chemistry Panel includes the following analytes:

- Sodium
- Potassium
- BUN/Urea
- Creatinine
- Glucose
- Calcium
- Phosphorus
- Total Protein
- Albumin
- AST(SGOT)
- ALT(SGPT)
- Alkaline Phosphatase

Hematology Panel includes:

- WBC
- Haemoglobin
- Haematocrit
- RBC
- MCV
- MCH
- MCHC
- RDW
- Platelet Count
- Differential (% and absolute)

Urine pregnancy test in women of child bearing potential (Visits 1, 4 and Early Termination, if applicable).

A serum potassium test will also be done at Visit 3.

APPENDIX VI: DROP INSTILLATION COMFORT MEASUREMENT

An evaluation of the comfort of the instillation of eye drops will be assessed for the Fellow Eyeonly within 5 minutes following in-clinic dosing at Visits 1, 2, AND 3.

The subject will be asked the following question upon instillation of the study drug:

'Did you experience any discomfort when placing the drops in your right/left eye?" Note: Personnel should indicate which eye is the Fellow Eye when asking this question.

The response to the question will be graded using the following scale:

- 1 = None
- 2 Mild
- 3 = Moderate
- 4= Severe

Note: The drop instillation comfort response is NOT considered an AE regardless of severity unless it results in an interruption of study drug treatment or discontinuation of the subject from the study.

If the subject is experiencing discomfort symptoms 5-15 minutes after the drop comfort assessment is completed, then the site should record these symptoms as AEs.

1. INTRODUCTION

This document describes the statistical methods and data presentations to be used in the summary and analysis of data from Protocol P-321-202. Background information is provided for the overall study design and objectives. The reader is referred to the study protocol and case report forms (CRFs) for details of study conduct and data collection.

1.1. STUDY OVERVIEW

This is a multi-center, randomized, double-masked, placebo-controlled, parallel group Phase 2b trial designed to evaluate symptoms and signs in subjects with mild to moderate dry eye disease. It is anticipated that approximately 125 subjects with dry eye will need to be screened in order to randomize about 65 subjects and complete approximately 60 subjects. Subjects who meet inclusion/exclusion criteria will be enrolled in a single-masked placebo run-in period for up to 14 days. At the end of the run-in period, eligible subjects will be randomly assigned in a double-masked fashion to receive either 0.017% P-321 Ophthalmic Solution or Placebo TID for 28 days. The study will consist of four study visits and a follow up phone call: Visit 1 (Screening Visit), Visit 2 (Randomization and Treatment Day 1), Visit 3 (Treatment Day 15) and Visit 4 (Day 29, after 28 days of treatment) and a follow up phone call 5-9 days later. Three phone calls to remind subjects of dosing regimen and to inquire about adverse effects will also be done during the study and will occur between Visits 1 and 2, Visits 2 and 3, and Visits 3 and 4. The placebo-run-in is single-masked in that the subjects will remain masked to the treatment during the placebo run-in. However, the treatment is known to the investigator, medical monitor, study site personnel, and those involved in the conduct of the study. The randomized treatment assignments are double-masked in that the treatment will be masked to the investigator, medical monitor, study site personnel, subjects in the study and those involved in the conduct of the study.

This study is designed to evaluate the changes in symptoms and signs of dry eye disease including conjunctival staining of the lid wiper area of the upper eyelid (with photographs if technology is available), corneal staining, bulbar conjunctival staining, and tear break-up-time (TBUT). Dry eye symptom questionnaires including the Symptom Assessment in Dry Eye questionnaire (SANDE), the Standard Patient Evaluation of Eye Dryness (SPEED) questionnaire, and a 7-item symptom questionnaire will be completed at each visit prior to other assessments. Exploratory assessments of expression of biomarkers of inflammation in the tears and from impression cytology samples collected from the lid wiper and the bulbar conjunctiva will be performed.

Safety will be assessed throughout the study by adverse event monitoring, biomicroscopy and external eye examination, best corrected visual acuity (BCVA), physical examinations, vital signs, clinical laboratory tests, and an assessment of comfort after taking the medication in-clinic.

Eligible subjects will have at least one eye that meets the entry criteria. This will be referred to as the Study Eye. For the purpose of efficacy analysis in this trial, each subject will have only one Study Eye. If a subject has only one qualifying eye, this eye will be the Study Eye. If both eyes of the subject qualify, then the Study Eye will be the eye with the highest total corneal staining score at Visit 1. If the scores for total corneal staining are the same, the Study Eye will be the right eye. The non-Study Eye is referred to as the Fellow Eye.

1.2. SCHEDULE OF VISITS AND PROCEDURES

	Visit 1	Phone call	Visit 2	Phone Call	Visit 3	Phone call	Visit 4	ET	Follow up
Event	Screening Visit Day -14	Day -7 ± 1 to Day 1	Randomization -Treatment Day 1	Day 8 ± 1	Treatment Day 15	Day 22±	Day 29	Early Termination Visit	Follow up call 7 days ± 2 after Visit 4
Informed Consent	X								
Eligibility criteria reviewed	X		X						
Medical History/Changes	X		X		X		X	X	X
Concomitant Medication/Changes	Xª		X		X		X	X	X
Abbreviated Physical Exam	X						X	X	
Vital Signs	X		X		X		X	X	
Urine Pregnancy Test	X						X	X	
Serum Chemistry, Hematology	X				Xb		X	X	
Dry Eye Symptoms ^c	X		X		X		X		

	Visit 1	Phone call	Visit 2	Phone Call	Visit 3	Phone call	Visit 4	ET	Follow up
Event	Screening Visit Day -14	Day -7 ± 1 to Day 1	Randomization -Treatment Day 1	Day 8 ± 1	Treatment Day 15	Day 22±	Day 29	Early Termination Visit	Follow up call 7 days ± 2 after Visit 4
Study Medication Instillation Technique Training/Observation in Clinic	X ^d		Xe		Xe				
Dispense Study Medication	X ^d		Xe		Xe				
Drop Instillation Comfort Assessment ^f	X		X		X				
Subject reminder for when to take medication		X		X		X			
Collect Returned Study Medication			X ^d		Xe		Xe	Xe	
Best Corrected Visual Acuity	X		X				X		
Biomicroscopy and External Eye Examination	X		X		X		X	X	
Tear osmolarity & Meibomian gland assessment ^g	X								
Tear Collection for Biomarker ^h			X		X		X		

	Visit 1	Phone call	Visit 2	Phone Call	Visit 3	Phone call	Visit 4	ET	Follow up
Event	Screening Visit Day -14	Day -7 ± 1 to Day 1	Randomization -Treatment Day 1	Day 8 ± 1	Treatment Day 15	Day 22±	Day 29	Early Termination Visit	Follow up call 7 days ± 2 after Visit 4
TBUT	X		X		X		X		
Corneal Staining	X		X		X		X		
Bulbar Conjunctival Staining	X		X		X		X		
Lid wiper staining of the upper eyelid ⁱ	X		X		X		X		
Impression Cytology ^j			X				X		
Schirmer's Test (unanesthetized)	X								
Intraocular Pressure	X								
Adverse Event Monitoring	X	X	X	X	X	X	X	X	X

- a. Concomitant medications taken within 28 days of screening will be reviewed
- b. Only serum potassium
- c. Dry eye symptom questionnaires (SANDE, SPEED, and 7-item symptom questionnaire) will be completed as ordered before any other study assessments are performed at each visit. SANDE Part 1 will be completed at Visits 1-4, and Part 2 will be completed at Visits 2, 3, and 4.
- d. Placebo run-in study medication only
- e. Double-masked study medication per assigned subject treatment number
- f. To be assessed within 5 minutes after dosing in clinic for the Fellow Eye only
- g. Meibomian gland assessment to include clinical gland evaluation ± meibography (if available). If available, photographs will become part of the source and electronic data.
- h. Must be completed before any ocular staining has occurred. Tears from the Study eye for prostaglandins and from the Fellow Eye for MMP-9activity
- i. Lid wiper staining may include photographs if technology is available. If available, photographs will become part of the source and electronic data.
- j. Must be conducted after corneal, conjunctival and lid wiper staining and will be done in the Study Eye only

1.3. GLOSSARY OF ABBREVIATION

AE Adverse event

ANCOVA Analysis of Covariance
BCVA Best corrected visual acuity

CRF Case report form IOP Intraocular pressure

MedDRA Medical Dictionary for Regulatory Activities

MGD Meibomian gland dysfunction mITT Modified Intent-to-Treat

SANDE Symptom Assessment in Dry Eye questionnaire

SPEED Standard Patient Evaluation of Eye Dryness questionnaire

TEAE Treatment emergent adverse event

TBUT Tear break-up time
WHO World Health Organization

2. OBJECTIVES

Primary Objective:

The primary objective is to evaluate the efficacy of treatment with 0.017% P-321 taken TID in subjects with mild to moderate dry eye disease after 28 days of treatment on Dry Eye Symptoms.

Secondary Objectives:

The secondary objectives are to evaluate the safety and tolerability of 0.017% P-321 taken TID in subjects with mild to moderate dry eye disease.

Exploratory Objective:

The exploratory objective is to evaluate the expression of biomarkers of inflammation in tears and from impression cytology samples collected from the lid wiper and the bulbar conjunctiva.

3. GENERAL STATISTICAL CONSIDERATIONS

3.1. SAMPLE SIZE AND POWER

A sample size of approximately 65 randomized subjects is proposed. Assuming a dropout rate prior to Visit 3 of 10%, this provides approximately 60 subjects with post-baseline data. The sample size estimation was based on assumptions about the standard deviation and treatment effect for the change from baseline SANDE global score (Part 2 assessment) from a previous study, protocol P-321-101. At Day 28, the pooled standard deviation for the change from baseline was 22 and the difference in means was 20, representing a standard effect size of 0.9. If the true standard deviation is 22, a sample size of 30 subjects per group will provide at least 90% power to detect a true difference in means of 20 using a two-sided hypothesis test with Type 1 error of 5%. All else being equal, this sample size provides at least 70% power if the treatment difference is at least 15 units or if the standard deviation is no more than 29.

3.2. RANDOMIZATION AND MASKING

For the placebo run-in portion of the screening process, all subjects will receive a placebo vehicle. The placebo-run-in is single-masked in that the subjects will remain masked to treatment during the placebo run-in. However, the treatment is known to the investigator, medical monitor, study site personnel, and those involved in the conduct of the study.

Following the placebo-run-in period, approximately 65 subjects will be randomly assigned in a 1:1 allocation ratio to either 0.017% P-321 Ophthalmic Solution or placebo, stratified by clinical site. The randomized treatment assignments are double-masked in that the treatment will be masked to the investigator, medical monitor, study site personnel, subjects in the study and those involved in the conduct of the study.

CONFIDENTIAL Page 10 08 August 2017

3.3. HANDLING OF DATA

3.3.1. Strata and Covariates

All analyses of the primary and secondary efficacy endpoints will include site as a fixed effect in the statistical models. If the endpoint is a change from baseline endpoint, the baseline value will also be included as a covariate in the statistical model.

3.3.2. Examination of Subject Subsets

There are no planned subset analyses.

3.3.3. Multiple Testing and Comparisons

All analyses will be conducted without adjustments for multiple testing.

3.3.4. Missing Data and Outliers

Every effort will be made to obtain required data at each scheduled evaluation from all subjects. See section 3.3.5 for details of imputing missing dates. A sensitivity analysis will be performed for the primary endpoint imputing missing data by multiple imputation. See section 5.2.1 for details. Unless otherwise specified, other missing data will not be imputed.

3.3.5. Imputation of Incomplete Dates

An incomplete date is any date for which either the day, month or year is unknown, but all three fields are not unknown. An incomplete date occurs when the exact date an event occurred or ended cannot be obtained from a subject. For many of the analyses, a complete date is necessary in order to determine if the event should be included in the analysis (i.e., if the event is treatment-emergent) or to establish the duration of an event. In such cases, incomplete dates will be imputed.

For purposes of imputation, all events with an incomplete end date are assumed to have ended on or before the day the form was completed. In an effort to minimize bias, the project statistician will impute dates in a systematic, but reasonable manner. For missing dates during the placebo run-in phase, if the month/year is the same as the Day -14 month/year then the date will be set to the date of Day -14. In other cases, missing days will be imputed as the day component of Day -14; missing months/years will be imputed as the month/year of Day -14. For missing dates during the double-masked phase, if the month/year is the same as the Day 1 month/year then the date will be set to the date of Day 1. In other cases, missing days will be imputed as the day component of Day 1; missing months/years will be imputed as the month/year of Day 1. A list of incomplete and imputed dates will be prepared by the project statistician or statistical programmer(s) and will be submitted for review by the clinical project manager and sponsor.

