7.1 Visit 1: Screening Day -14 (14 days prior to Visit 2)

Procedures will be completed at Visit 1 in the following general order. The visit will start between approximately 8:00AM and 11:00AM. All subjects who sign an informed consent document will be assigned a unique 6-digit screening number (i.e., XXX-XXX, which will be a compilation of the site number (first 3 digits) and subject number (last 3 digits). This subject number will be unique within this trial and will be used to identify the subject throughout the study.

- Obtain written informed consent
- Administer ocular symptom questionnaires (SANDE Part 1 only, SPEED, and a 7-item symptom questionnaire) before other procedures
- Review of the medical history
- Review concomitant medication history in the past 28 days
- Vital signs (pulse, blood pressure, temperature and respiration rate), height and weight
- BCVA
- Biomicroscopy and external eye examination
- Tear osmolarity
- TBUT
- Assessment of Meibomian glands
- Staining procedures conducted in the following order (refer to Manual of Procedures):
 - Corneal staining
 - o Bulbar conjunctival staining
 - Staining of the lid wiper area of the upper eyelid (with photographs taken if technology is available)
- Abbreviated physical exam (including eyes, ears, nose, throat (EENT), respiratory, cardiovascular, musculoskeletal, gastrointestinal, and dermatological)
- Collect blood for Hematology and Chemistry
- Urine pregnancy test (women of child-bearing potential only)
- Schirmer's test
- IOP)
- Review eligibility criteria
- Once all other procedures and assessments have been completed, review the qualification criteria and if the subject qualifies for the study, determine which eye is the Study Eye
- Instruct subject in study drug instillation technique and observe/correct technique using study drug dispensed at this visit.
- Complete drop instillation comfort questionnaire within 5 minutes after dosing for the Fellow Eye (the non-study eye)
- Assess adverse events during this visit

• At the end of the visit, the subject will be scheduled for Visit 2, 14 days from this visit, will receive their study medication to take home, and provided with the instructions in Section 7.1.1.

In the event that the subject does not qualify at Visit 1, the subject may be rescreened.

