4.2. SAFETY POPULATION

The Safety Population will include all subjects who receive at least one dose of double-masked study medication in either eye. All safety analyses for the double-masked portion of the study will be conducted on the Safety Population, analyzed as treated.

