5.3.1. Adverse Events

Adverse events will be mapped to a Medical Dictionary for Regulatory Activities (MedDRA) version 19.1 preferred term and system organ classification. If a subject experiences multiple events that map to a single preferred term, the greatest severity grade and strongest investigator assessment of relation to study medication will be assigned to the preferred term for the appropriate summaries. Should an event have a missing severity or relationship, it will be classified as having the highest severity and/or strongest relationship to study medication. Summaries of incidence rates (frequencies and percentages) of individual AEs by MedDRA system organ class and preferred term will be prepared. Such summaries will be displayed for all TEAEs, TEAEs by maximum severity, and TEAEs by strongest relationship to study drug. Serious AEs and AEs leading to discontinuation of study drug will also be summarized. Separate summaries will be performed for those AEs occurring during the placebo run-in period.

All adverse events reported will be listed for individual subjects showing both verbatim and preferred terms. AEs will be flagged by run-in or double-masked treatment period as appropriate.

Any adverse event with a missing onset date will be considered to be a TEAE occurring during the double-masked treatment period.

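### SAP 3.3.5 imputes some partly dated run-in adverse events to Study Day 15–18, or to a date that does not exist, so they can be counted as double-masked TEAEs

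*SAP*

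**What the plan says.** SAP 3.3.5 has one rule for each study phase. The run-in rule opens with the words "For missing dates during the placebo run-in phase". A partial date that shares its month with Day -14 is moved to Day -14 itself. Where the month differs, the rule reads: "In other cases, missing days will be imputed as the day component of Day -14". The double-masked rule has the same form: "In other cases, missing days will be imputed as the day component of Day 1". The section covers dates on which an event began or ended, and it gives its reason: "complete date is necessary in order to determine if the event should be included in the analysis (i.e., if the event is treatment-emergent"). A list of incomplete and imputed dates goes to the clinical project manager and the sponsor for review.

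SAP 3.3.7 defines a double-masked TEAE by onset, or worsening, after the first double-masked dose. SAP 5.3.1 flags AEs by period without saying what sets the flag, and adds: "Any adverse event with a missing onset date will be considered to be a TEAE occurring during the double-masked treatment period". Under SAP 4.2, "The Safety Population will include all subjects who receive at least one dose of double-masked study medication in either eye".

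**The concern.** The run-in lasts about two weeks. Keeping the day number of Day -14 and moving to the next month adds a whole calendar month, so the result overshoots the run-in. Section 3.3.5 does not cap the imputed onset before Day 1, and it has no provision for a day number that the month lacks.

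What is at stake is the separation of the two periods. The protocol synopsis requires the safety of the run-in and double-masked periods to be analysed separately, and the SAP plans separate TEAE tables. If the period is derived from the imputed onset, an event on run-in placebo enters the double-masked table, in whichever arm the subject was later assigned.

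**Working it through.** The documents give no figure on this point, so there is none to reproduce. The check is calendar arithmetic.

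**Inputs**
- Run-in length k = 14 days. Protocol 7.1 heads Visit 1 as "Screening Day -14 (14 days prior to Visit 2"). SAP 1.1 says up to 14 days, so k is varied below.
- Study Day after Day 1 = event date − Day 1 + 1 (SAP 3.3.7).
- L = number of days in the calendar month that contains Day -14.

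**Run-in rule.** The same day number in the next month is L days after Day -14, and Day 1 is k days after Day -14. So the imputed Study Day = L − k + 1. With k = 14:
- L = 31: 31 − 14 + 1 = 18
- L = 30: 30 − 14 + 1 = 17
- L = 29: 29 − 14 + 1 = 16
- L = 28: 28 − 14 + 1 = 15

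*Example.* Day -14 is 25 January 2017 and Day 1 is 8 February. A run-in event recorded only as February must have occurred on 1–7 February. The rule dates it 25 February, which is Study Day 18.

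**How often the calendar exposes it.** Take all 365 Visit 1 dates from 1 October 2016. A 14-day run-in reaches a second month for the last 13 start dates of each month: 13 × 12 = 156 of 365 (43%).

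| Month of Day -14 | Start dates | Result |
|---|---|---|
| Seven 31-day months | 91 | Day 18: 84; no such date: 7 |
| Four 30-day months | 52 | Day 17: 52 |
| February 2017 | 13 | Day 15: 13 |

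That is 149 valid dates, all after Day 1, and 7 non-existent ones (Visit 1 on 31 October, 29, 30 or 31 January, 31 March, 31 May or 31 August). None falls inside the run-in.

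**Sensitivity to k.** The same formula gives Day 19–22 for k = 10, 17–20 for k = 12, 16–19 for k = 13 and 13–16 for k = 16. Every valid date is still after Day 1.

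**Share of run-in days exposed.** Only run-in days in the second month matter: (1 + 2 + … + 13) × 12 = 91 × 12 = 1,092 of 365 × 14 = 5,110, or 21%. The event must also have a known month and a missing day.

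**Size of one error.** One misassigned event in a new subject moves an arm's incidence by 1/30 = 3.3 points, or 1/32.5 = 3.1 points if all 65 randomized subjects are dosed.

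**Double-masked rule.** A partial date in the month after Day 1 goes to Study Day L + 1. The 28 treatment days cross a month end for 27 × 12 = 324 of 365 start dates (89%): Day 32 for 182, Day 31 for 108, Day 29 for 27, and no such date for 7. Dosing is scheduled through the day before Visit 4 (Day 29), so each valid date falls after the last scheduled dose.

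**End dates.** The same rule serves onset and end. Suppose Day 1 is 8 February, onset is 12 February and the end is recorded only as February. The end is set to 8 February, four days before onset.

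**Events with no onset date.** Section 5.3.1 sends them all to the double-masked period. A subject who fails at Visit 2 never receives double-masked drug, so is outside the Safety Population on which the double-masked TEAE tables are run. Read literally, that event is in neither period's TEAE table, although it is still listed.

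**The case against.** The strongest reply is that the rule applies only to events already placed in the run-in. AEs are flagged by period, and Protocol 7.3 has AEs since the last visit assessed at Visit 2 before the first double-masked dose. On that reading the event stays in the run-in table. This stands as a possible reading, so a reader who infers that such events always become double-masked TEAEs goes further than the text. But the SAP does not say that the known phase overrides the imputed date. The stated purpose of imputation points the other way, and the AE data items in Protocol 10.1 include a date of first occurrence but no period field. Even if the flag prevails, the onset date is impossible for a run-in event.

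A reader might also infer that the imputed day is always 15–18. That holds only for valid dates and a run-in of exactly 14 days.

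Further points stand against a larger claim:
- The list of imputed dates is reviewed, although no correction rule is given, and listings show partial dates as recorded.
- Subjects are contacted about weekly over some 50 days, so partial dates should be uncommon.
- Run-in events precede randomization, so leakage is not expected to favour either arm.
- A double-masked event moved to Day 29–32 remains a TEAE in the correct arm, because the definition has no upper time limit. No AE duration table is planned.

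**Conclusion.** The rule is wrong as written. For a 14-day run-in that reaches a second month, a run-in event with the day missing and the second month recorded gets Study Day 15–18 (149 of 156 Visit 1 dates) or a date that does not exist (7 of 156). It can be counted as a double-masked TEAE if the period is derived from the imputed onset, and the SAP leaves that open.

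The double-masked and end-date faults distort onset and duration but change no planned incidence table. The undated event in a run-in failure is a real but rare gap.

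Severity is minor. No efficacy analysis is touched, and same-month partial onsets stay in the correct period. The documents give no count of partial dates, so the 3-point shift describes one hypothetical event, not an expected bias. The counts assume Visit 1 dates spread over a year from October 2016; the day range depends only on run-in length and month length.

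**What to change.** In SAP 3.3.5:
- For an onset with the day missing, use the later of the first day of the recorded month and the first dose date of the period in which the event was recorded. Keep run-in onsets before Day 1 and no later than any known end date. In the example this gives 1 February, inside the run-in. It does so for every run-in that crosses a month end, and it cannot produce a non-existent date.
- For an end with the day missing, use the last day of the month, capped at last contact.
- State that the recorded period decides the table, and say what sets it, such as the visit at which the event was reported.

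In SAP 5.3.1, assign an AE with no onset date to the double-masked period only if the subject received double-masked drug, and otherwise to the run-in. Align the matching sentence in 3.3.7.

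The cost is a few sentences and the corresponding programming. No new data are needed, assuming that the reporting visit can be recovered from the CRF, which the documents do not state.
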